DNA	Deoxyribonucleic acid
GCP	Good clinical practice
ECM	Embryo culture medium
ICH	International Council for Harmonization of Technical Requirements for Pharmaceuticals for Human Use
ICSI	Intracytoplasmic sperm injection
IEC	Independent ethics committee
IRB	Institutional review board
IVF	In vitro fertilization
IVI RMA	Instituto Valenciano de Infertilidade / Reproductive Medicine Associates
NMR	Nuclear magnetic resonance
PGT-A	Preimplantation genetic test for aneuploidy
SIVIS	Software for medical record management

AIM: main objective/research question

Main objective:

To evaluate whether nuclear magnetic resonance (NMR) spectroscopy can assist in the prediction of ploidy of pre-implantation embryos (euploidy vs aneuploidy).

Research question:

Is NMR able to identify a differential metabolic pattern between aneuploid and euploid embryos in order to improve embryo selection?

Is there a metabolic profile difference between an embryo with 3 days of culture and the same embryo after 5 or 6 days of culture?

Introduction

A. Background

Worldwide, infertility affects around 15% of the couples in reproductive age. The ability to procreate is largely a female-age limited process, with one in eight women experiencing infertility, a proportion that is even higher among women aged 35 or older. Assisted reproductive technologies (ART) are of paramount importance for these couples, and in many they are the only solution to constitute a family (1).

The optimal scenario in ART is a single-embryo transfer (SET) followed by the delivery of a healthy baby. For this reason, multiple laboratory technical approaches have been developed to improve the selection of the best embryo available. Currently, this selection process is largely based on morphologic assessment. This type of evaluation, however, appears to be insufficient since many apparently top quality embryos ultimately do not implant or eventually result in a miscarriage. One of the main reasons for this is the fact that up to 70% of the embryos considered viable from a morphological perspective present an abnormal number of chromosomes and are, therefore, generally not compatible with life (2).

One means to overcome this issue is to perform preimplantation genetic testing of embryos to detect aneuploidy (PGT-A), which entails the removal of a small number of cells for analysis by either next-generation screening or comparative genomic hybridization (3). However, this analysis has the disadvantage of being invasive, time-consuming and expensive. Thus, the search for an efficient alternative selection method during the preimplantation stage which could improve the success rate of ART while decreasing the cost and time required to select chromosomally normal embryos as best as possible continues.

A suitable alternative to PGT-A could rely on the characterization of the metabolic profile of the embryo culture medium (ECM) by NMR, a non-invasive, rapid, economic and sensitive technique which is already currently clinically applicable. The conceptual basis of this approach has been described in a previous publication performed after a day 3 embryo biopsy, which demonstrated that embryos with chromosomal abnormalities presented a different metabolic pattern and, consequently, a different ECM composition (4). However, this study is of limited value, since it has been demonstrated that embryos are able to self-correct chromosomal errors found by day 3, whereby the current recommendation is for PGT-A to be performed on day 5 (or day 6). Further studies are needed to assess the usefulness of NMR for prediction of the ploidy of pre-implantation embryos.

B. Justification and translational potential to the clinic and impact on patient's care improvement:

This research study aims to validate the ECM analysis by NMR spectroscopy, as a faster and less-costly alternative to PGT-A which could significantly enhance embryo selection and the success rate of ART.

Methodology

A. Study Design

We propose a single-center prospective sibling case-control pilot study. In summary, all consenting patients will undergo in vitro fertilization (IVF) followed by PGT-A according to normal clinical practice. While the overall procedures towards PGT-A will not change, we will request that they consent additionally to donate the embryo culture medium, which otherwise would be discarded, for investigational purposes. The study will be conducted in conformance with Good Clinical Practices (GCP).

B. Study period and context

Women who will undergo IVF followed by PGT-A at the Reproductive Medicine Clinic of IVI RMA Lisboa will be screened each day by a study collaborator and treating physician. Eligible women will be invited to participate in the study and provided written patient information on the trial (pre-screening visit). Those who accept to participate will be requested to sign written informed consent (screening/inclusion visit).

The on-study period is planned to have an overall duration of approximately 4 weeks with 2 visits for each subject, as detailed in Fig 1. The on-study period starts on the day that informed consent is signed, which can occur up to the day of patient oocyte retrieval, and ends when the results of the PGT-A procedure are known. More information regarding the overall recruitment plan, exposure, monitoring and data collection are described below.

[figure not shown]

Figure 1 – overall on-study period scheme

C. Reference Population

Our target population are healthy women who will undergo a IVF followed by PGT-A. This study will evaluate embryo culture medium compositions of 50 aneuploid embryos, 50 euploid embryos, and 30 controls (no-embryo culture medium).

D. Subject Inclusion/exclusion criteria and case-control matching

The subject inclusion and exclusion criteria are summarized in Table .

Inclusion criteria	Exclusion criteria

 Age: ≥ 18 and < 49 years old. Body Mass Index (BMI) ≥ 18.5 Kg/m² and < 30 Kg/m². Planned for IVF followed by PGT-A. Oocytes retrieval and fertilization by ICSI Six follicles over 14 mm on the day of the triggering. Signed and dated informed consent. 	
 Previous history of poor ovarian response (< 4 oocytes retrieved) with a maximal dose of ovarian stimulation (≥ 300 IU/day). Presence of a medical condition which is known to affect ART outcome (e.g. thyroid dysfunction). Current use of anti-depressants, anti-psychotics, steroids, antiepileptics or chemotherapy. Those unable to comprehend the investigational nature of the proposed study.

Table 1 – Study inclusion and exclusion criteria

E. Intervention and Follow-up

Ovarian stimulation, oocyte retrieval, all embryology procedures and PGT-A will be performed according to how they are normally performed in IVI Lisboa. Women will start ovarian stimulation with either recombinant follicle-stimulating hormone (Gonal F, Puregon, Pergoveris, Bemfol, Ovaleap or Elonva) or highly purified human menopausal gonadotrophin (Menopur). Women will be submitted to pituitary down regulation, through daily administrations of either cetrorelix or ganirelix (GnRH antagonist) or oral progestogens (desogestrel) in either a fixed or flexible protocol. Cycles will be monitored by vaginal ultrasound scans and serum determination of estradiol and progesterone. Once three follicles of ≥ 17 mm are observed, oocyte maturation will be triggered with a GnRH agonist (0.3 mg decapeptyl). Cumulus-oocyte complexes will be collected by transvaginal aspiration 35-36 h after hCG administration (5). Oocytes will be denuded and ICSI will be performed at least 4 hours after the pick up to all mature oocytes. Fertilized oocytes will be cultured in the IVF laboratory incubators until they reach blastocyst stage. The ones presented good morphology will be biopsied, according to the ASEBIR embryo classification (6). After biopsy embryos will be frozen and the trophoctoderm cells will be analyzed by next generation sequencing (NGS) to identify aneuploidies. Culture media where each embryo developed will be analyzed via NMR Spectroscopy in order to evaluate the metabolomic profile and compare it with the chromosomic analysis.

The study period includes the following visits to the clinic and procedures:

VISIT 0 (PRE-SCREENING VISIT)

- The study coordinator will contact potential participants in our center. Information regarding the study will be provided followed by an invitation to participate in this study.

VISIT 1 (SCREENING AND STUDY INCLUSION)

- Participants will sign and date the informed consent.
- Collection of demographic and anthropometric data, medical and surgical history
- Verification of eligibility criteria check list.
- As described in more detail below, the culture medium from euploid and aneuploid embryos will be collected and then analyzed by NMR.

F. Study restrictions

During the study, patients are restricted to use any type of medication that may interfere with ovarian stimulation or embryology. Specifically, current use of anti-depressants, anti-psychotics, steroids, antiepileptics or chemotherapy constitute an exclusion criterion for study participation.

G. Participant withdrawal and protocol violation

Participants may withdraw from the study at any time. Eligible participants who gave adequate consent to the study and later withdraw will be replaced. Whenever a participant does not follow the planned protocol, this will be considered as a protocol violation. Given the pilot and explanatory nature of the study, these subjects will be excluded from the analysis with justification.

H. Potential advantages and financial incentives for the participating subjects

Beyond the potential clinical advantage of the study in the future, no other clinical or financial incentive will be provided for the participating subject.

I. Collection, selection, analysis and destruction of biological samples and information

BIOLOGICAL SAMPLE GATHER PROTOCOL AND OBJECTIVE OF SAMPLE COLLECTION

ECM collection

After embryo biopsy, a minimum quantity of 25 uL of embryo culture medium will be collected at Day 3 and Day 5 (or Day 6) of embryos development. Collection of the media, will be carried out by pipetting culture

media into Eppendorf tubes which will be immediately centrifugated in a mini centrifuge during 1 minute to remove cell contamination. Supernatant will be collected to a new tube with phosphate buffer, D2O and sodium azide to prevent bacterial and fungi development. Samples will be immediately anonymized, as described below, and frozen in liquid nitrogen and then stored at -20 °C at IVI RMA Lisboa. Samples will be transferred in dry ice to ITQB, which is located at [name]. [name] will be responsible for the collection and storage of samples at IVI Lisboa. This facility has a 24-hour security system in place and access to the storage area is restricted to authorized personnel only.

Selection process of case-control sibling embryo culture media

In order to minimize potential confounding, paired-sibling embryo culture media (two samples derived from the same patient and treatment cycle) will be allocated in pairs and in a 1:1 ratio to each study group. The pair-sibling allocation will be performing after the results of the PGT-A procedure are known. Pairing will be performed preferably using embryos with similar developmental staging and morphological grading.

Finally, each patient can include up to 3 pairs of sibling culture media in the analysis. The remaining samples will be immediately destroyed.

NMR procedure

ECM samples will be thawed at room temperature before analysis, will be transferred to a 1.7-mm NMR capillary shigemi tube for analysis. The NMR spectra will be acquired in a BrukerAvance II 500 spectrometer (BrukerBiospin) equipped with a prodigy TCI cryoprobe. All experiments will be acquired at 298 K. For each sample, two ¹H-NMR spectra will be obtained: a Carr-Purcell-Meiboom-Gill (CPMG) spin echo pulse sequence, which generates spectra edited by T2 relaxation times to reduce signals from high molecular weight species and to facilitate the detection of low molecular weight species, and a 1D NOESY pulse sequence, which generates an unedited spectrum with improved solvent peak suppression (extremely useful for the observation of signals near the water resonance). The spectra will be processed by a Fourier Transform and multiplied by an exponential function using Topspin 4.0. Phase correction, baseline correction and spectra calibration (methyl group signal of the lactate at a chemical shift 1.32 ppm) will be performed before further analysis. Metabolites will be quantified with ChenomxNmrSuite 8.0.2 using the Human Metabolites Database as reference. This software allows the deconvolution of the NMR spectra and the determination of the

metabolite concentrations. From the previous studies it is expectable that we will be able of determine around 20 to 30 metabolites including aminoacids, fatty acids and carbohydrates like sucrose, glucose and pyruvate.

The samples analysed in this study will be destroyed immediately upon analysis.

SAMPLE IDENTIFICATION PROTOCOL

All consenting subjects will be given a unique screening number (eg. 037-SN-0X). Each participant will be assigned only one screening number. Screening numbers will not be re-used for different participants.

Samples (ECM) will be collected and identified immediately using sticker labels. These labels contain a single anonymized identifying code with the following format: <STUDY CODE> <SUBJECT NUMBER> <TYPE OF SAMPLE> <SUBJECT YEAR OF BIRTH> <SAMPLE DATE>. For example, the identifying code 2004-LIS-037-SN-01-ECM_D3-1983-30042020 provides the following information:

- <STUDY CODE>: internal reference code of study (2004-LIS-037-SN)
- <SUBJECT NUMBER>: 0X
- <TYPE OF SAMPLE>: ECM_DX (X = day 3 or day 5/ day 6)
- <SUBJECT YEAR OF BIRTH>: coded as YYYY;
- <SAMPLE DATE>: date the sample was collected, coded as DDMMYYYY.

Statistical methodology

A. Data base

Data will be collected in a secure and encrypted case report form system created specifically for the study hosted on a dedicated server firewall-protected serve. The database will be rigorously defined with the variables destined to be analyzed according to the described study objectives and will have inbuilt validation procedures to ensure the correct introduction of data and avoid cases of missing information where such is not applicable. The study team collaborating in the study will be responsible for the data collection. These anonymized data will be stored for at least an additional 25 years.

In accordance with Portuguese law, all data exported for statistical analysis will be anonymized to protect the clinical and personal information of the subjects. Finally, and prior to the statistical study, an exploratory data analysis will be carried out to review the quality of the information extracted.

B. Study Variables

MAIN-OUTCOME MEASURES (DEPENDENT)

The primary outcome of this study is the assessment of different metabolic profiles between culture medium of euploid versus aneuploid embryos.

EXPOSURE VARIABLES (INDEPENDENT)

The metabolic profile of culture medium of euploid and aneuploid embryos will be compared to culture medium without embryo (control).

CONTROL VARIABLES

The following variables will be recorded during the analysis (as continuous variables, unless mentioned otherwise):

- Female subject age (in years).
- Male subject age (in years)
- Female body mass index.
- Menstrual cycle length.
- Number of preceding ART cycles.
- Duration of infertility (in years).
- Infertility diagnoses (tubal, ovulatory, endometriosis, male factor or otherwise unexplained).
- Baseline AMH.
- Baseline AFC.
- Number of follicles >11 mm on the day of ovulation triggering.
- Total dose of exogenous gonadotropins.
- Total duration of OS.
- Number of oocytes retrieved.
- Number of fertilized oocytes.
- Number of embryos available for biopsy.
- Quality of each embryo available for biopsy.
- Number of euploid and aneuploid embryos.

C. Sample Size

Owing to the exploratory nature of the study, we are unable to determine an accurate sample size for this study hypothesis. Hence, we elected to recruit a pre specified number of a maximum of 50 subjects (donating a minimum of a pair of sibling culture media).

D. Statistical data analysis

EXPLORATORY DATA ANALYSIS

Basic demographic characteristics will be compared amongst the study who did and did not have a spontaneous miscarriage using the t-student/Mann-Whitney test (for continuous variables, according to the normality of the distribution) or Fisher's Exact test (for categorical variables).

HOMOGENEITY ANALYSIS

In order to minimize potential confounding, paired-sibling embryo culture media (two samples derived from the same patient and treatment cycle) will be allocated in pairs and in a 1:1 ratio to each study group. The pair-sibling allocation will be performing after the results of the PGT-A procedure are known.

OBJECTIVES ASSESSMENT

Considering that we will be able to identify around 20 to 30 metabolites, the minimum number of samples per group for a False Discovery Rate (FDR) of 5% is 40 samples, this value was calculated using the default parameters of MetSizeR (7), a software that allows sample size calculation for metabolomic studies. Assuming that a pre-specified proportion of at least 10% metabolites will be predictive of the outcome, the estimated power to detect a statistically significant difference among the groups is >90%.

Metabolite concentration will be used for univariate and multivariate analysis. In the univariate analysis, data normality will be checked by Shapiro test. Two-sample t-test, if the data has normal behavior, or Wilcoxon-rank test, if the data has not a normal behavior. Comparisons will be performed to confirm the metabolite differences significance. In multivariate analysis, sample classification will be performed by Principal Component Analysis (PCA), Partial Least Squares Discriminant Analysis (PLS-DA), and Orthogonal Projections to Latent Structures (OPLS-DA) using R and Simca.

Pathway analysis will be performed in Metaboanalyst (www.metaboanalyst.ca) to identify which metabolic pathways are affected in aneuploid embryos. Pathway Analysis combines pathway enrichment analysis with pathway topology analysis, allowing identification of the most relevant pathways involved in aneuploidy. For that, it will be used the metabolite concentrations determined previously for the aneuploid embryos and controls; and human pathway library as reference.

Work plan

The pilot study workplan of the pilot phase includes three phases (ECM collection, ECM analysis by NMR and multivariable analysis), as detailed below.

	Months									
	1	2	3	4	5	6	7	8	9	10
Phase I - ECM collection										
Phase II - ECM analysis by NMR										
Phase III - Multivariable analysis										

The responsible persons for each phase are: I- [name]; II and III – [name]

Ethical issues

A. Ethical conduct of the study

This study will be submitted for approval by the Local Ethics Committee of IVI Lisboa. For the inclusion of all patients in the study, a signed informed consent is required, which must first be approved by this Ethics Committee.

This study respects the fundamental principles of the Declaration of Helsinki, the Council of Europe Convention on Human Rights and Biomedicine, the UNESCO Universal Declaration on the Human Genome and Human Rights, as well as the requirements of Portuguese law in the field of biomedical research, the protection of personal data and bioethics.

This study will be conducted in accordance with the ethical principles that have their origins in the Declaration of Helsinki and its most recent amendments, in compliance with the approved protocol, ICH-GCP guidelines, the EU Clinical Trial Regulation, and other national law(s) or regulatory requirements applicable in the countries where the study takes place.

B. Independent ethics committee /Institutional review board

Prior to the start of the study, the investigator is responsible for ensuring that the protocol and consent form have been reviewed and approved by a relevant IEC/IRB. The IEC/IRB shall be appropriately constituted and perform its functions in accordance with ICH-GCP guidelines and local requirements as applicable.

The IEC/IRB shall approve all protocol amendments (except for logistical or administrative changes), written informed consent documents updates, patient recruitment procedures (e.g. advertisements), written information to be provided to the patients, available safety information, information about payment and compensation available to patients, the investigator curriculum vitae and/or other evidence of qualification and any other documents requested by the IEC/IRB and Regulatory Authority (Competent Authority) as applicable.

C. Subject information and consent

The investigator will obtain a freely given written consent from each subject after an appropriate explanation of the aims, methods, anticipated benefits, potential hazards, and many other aspects of the study, which are relevant to the subject's decision to participate. The subject must be given ample time to consider participation in the study, before the consent is obtained. The informed consent form must be signed and dated by the subject and the investigator who has provided information to the subject regarding the study before the subject is exposed to any study-related procedure.

The investigator will explain that the subject is completely free to refuse to enter the study or to withdraw from it any time, without any consequences for her further care and without the need to justify her decision.

The subject will receive a copy of the informed consent documents.

The subjects will be informed about a new information and re-consent will be obtained.

D. Data Handling and Record Keeping

CASE REPORT FORMS/SOURCE DATA HANDLING

The study data must be verifiable with the source data, which requires access to all original records, laboratory reports and subject records. Therefore, the investigator must agree to allow access to subject records and the source data must be available for all study data. The subjects or their legal representatives must also allow access to the medical records of the subjects and they will be informed of this need and will express their agreement when they provide the informed consent.

The principal investigator will be responsible of maintaining the accuracy and authenticity of the clinical and laboratory data entered in the eCRF. Subject's source data will be data recorded by the embryologist, which will be kept in the clinical center where the study is carried out.

The investigator/center must allow direct access to the data / source documents (originals) for the activities related to the monitoring study, audit, review by the ethics committees (IEC/ IRB) and inspection by the regulatory authorities.

RETENTION OF ESSENTIAL DOCUMENTS

All records relating to the conduct of this study are to be retained by the investigator according to ICH, local regulations, or as specified in the clinical study agreement, whichever is longer. Prior to transfer or destruction

of these records, the Sponsor must be notified in writing and given the opportunity to further store such records. The investigator will allow representatives of Sponsor's monitoring members (and of the applicable regulatory authorities) to inspect all study records, eCRFs, and corresponding portions of the study patient's office and/or hospital medical records at regular intervals across the study. These inspections are for the purpose of verifying the adherence to the protocol, the completeness and accuracy of the data being filled in the eCRF, and compliance with applicable regulations.

E. Quality Assurance and Confidentiality

CONDUCT OF THE STUDY

The sponsor or designee will perform the quality assurance and quality control activities of this study, however, responsibility for the accuracy, completeness, and reliability of the study data presented to the Sponsor lies with the principal investigator generating data.

CONFIDENTIALITY

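### The only planned comparison of characteristics is by miscarriage, which the study does not observe; culture day (Day 5 or Day 6), which can differ within sibling pairs, is not matched, listed or adjusted for

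*Combined protocol and SAP*

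**What the plan says.** **Comparison of characteristics.** Statistical methodology D, Exploratory data analysis, has basic demographic characteristics "compared amongst the study who did and did not have a spontaneous miscarriage", using t, Mann-Whitney or Fisher tests. The Homogeneity analysis that follows says only that sibling media "will be allocated in pairs and in a 1:1 ratio to each study group". It contains no comparison.

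**Observation and groups.** Methodology B says the on-study period "ends when the results of the PGT-A procedure are known". Methodology E says "After biopsy embryos will be frozen". Statistical methodology B defines the primary outcome as the "assessment of different metabolic profiles between culture medium of euploid versus aneuploid embryos".

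**Sampling and pairing.** Under Methodology I, medium "will be collected at Day 3 and Day 5 (or Day 6) of embryos development". The selection process there adds: "Pairing will be performed preferably using embryos with similar developmental staging and morphological grading". The sample label has a type field, "ECM_DX (X = day 3 or day 5/ day 6"), and the collection date.

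**Variables and tests.** The control variables include the quality of each embryo available for biopsy, but not sampling day, culture hours or time since the last medium change. The univariate metabolite tests are two-sample t or Wilcoxon rank tests without covariates. PCA, PLS-DA and OPLS-DA are also named without a day term.

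**The concern.** There are two linked problems.

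First, the single sentence that compares characteristics uses a grouping the study cannot form and that is not the study's grouping. As written, the plan therefore contains no check that the euploid and aneuploid media are comparable.

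Second, the factors that need such a check belong to the embryo. A medium taken on Day 6 has had roughly 24 h more embryo metabolism than one taken on Day 5. The protocol itself treats culture time as a possible influence on the profile: its second research question asks whether Day 3 media differ from Day 5 or 6 media of the same embryo. If one ploidy group contains more Day 6 media, part of any metabolite difference would reflect duration of culture and not chromosomes, and nothing in the stated analysis would show it.

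**Working it through.** **1. Can the miscarriage groups be formed?** A miscarriage requires a transfer and a pregnancy. The study describes neither: embryos are frozen after biopsy, observation stops at the PGT-A result (about 4 weeks, 2 visits), and neither pregnancy nor miscarriage appears among the outcomes or control variables. The groups cannot be formed from the study's data.

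**2. Would ploidy groups repair the sentence?** No. Each pair comes from one patient and one cycle and contributes one medium to each group. Age, BMI, AMH and other patient-level variables are identical within a pair, so their difference by ploidy is zero by design.

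**3. What can still differ within a pair?** Sampling day, hours in the medium, stage and grade. Stage and grade are matched preferentially. Methodology E has embryos cultured until they reach blastocyst stage, so two siblings of equal stage and grade can satisfy the pairing rule with one sampled on Day 5 and the other on Day 6.

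**4. Illustration of size.** The plan has no figure of its own to reproduce here; its 40 samples per group does not bear on culture time.

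Input from the documents: 50 media per group (Methodology C).

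Assumed inputs, not in the documents:
- Metabolite turnover is proportional to time and carries through to the measured level. Day 6 is then +20% (144/120 h, medium not changed) to +50% (72/48 h, medium changed on Day 3).
- Within-day between-embryo CV is 20-30%.
- Day 6 share is 30% in one group and 40-50% in the other.
- There is no true ploidy effect, and the groups are treated as independent, as in the planned test.

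Formulas, in units of the within-day SD:
- Day 6 shift s = relative increase / CV
- Bias b = (p1 − p0) × s
- Variance in a group with Day 6 share p: v = 1 + s²p(1 − p)
- SE = √[(v0 + v1)/50]
- Rejection = Φ(b/SE − 1.96) + Φ(−b/SE − 1.96)

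| Case | s | b | v0, v1 | SE | Rejection |
|---|---|---|---|---|---|
| Equal shares, 30% v 30% | any | 0 | equal | – | 5.0% |
| +20%, CV 30%, 30% v 40% | 0.67 | 0.067 | 1.09, 1.11 | 0.210 | 6.2% |
| +50%, CV 20%, 30% v 40% | 2.5 | 0.25 | 2.31, 2.50 | 0.310 | 12.7% |
| +20%, CV 30%, 30% v 50% | 0.67 | 0.133 | 1.09, 1.11 | 0.210 | 9.7% |
| +50%, CV 20%, 30% v 50% | 2.5 | 0.50 | 2.31, 2.56 | 0.312 | 36.0% |
| +50%, CV 20%, 0% v 20% | 2.5 | 0.50 | 1.00, 2.00 | 0.245 | 53.2% |

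Simulating the t-test directly (20,000 runs per case) agrees: 6.1% for the second row, 35.8% for the fifth and 52.0% for the last. These are error rates per metabolite at 5%, before any FDR step.

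**The case against.** **The miscarriage sentence may be harmless.** It looks carried over from another protocol, and it touches neither the primary outcome nor any metabolite test. That is fair as to its direct effect. It still cannot be run, and no usable check stands in its place.

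**Stage is not ignored.** A reader might infer that stage and grade are simply left to confound ploidy. The documents do not support that: siblings are paired preferentially on both, and embryo quality is recorded. What stands is narrower. The preference has no criterion or fallback, nothing checks whether it succeeded, and equal stage does not mean equal time in culture.

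**Day is traceable.** A reader might also infer that the plan declares Day 5 and Day 6 to be one time point. It does not say so, and the label carries a day code and a date. The accurate statement is that no analysis separates the two days.

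**Direction is unknown.** It is tempting to say that aneuploid embryos reach biopsy later, so that a false signature will result. Nothing in the documents says so.

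**The size is easily overstated.** Dividing the bias by the within-day CV alone gives 0.50 SD and about 70% rejection at the extreme. That omits the variance added by mixing Day 5 and Day 6 media, which the two-sample test would see. In addition, for a nutrient only partly consumed, the relative change in concentration is smaller than the change in turnover, so the shifts assumed here may be too large for some metabolites.

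**Adjusting for stage may remove real signal.** If aneuploidy slows development, stage is partly a consequence of ploidy. This objection stands, and stage adjustment belongs in a sensitivity analysis. Culture hours differ in that they are known without NMR.

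**Conclusion.** The concern holds in this limited form. The miscarriage comparison is wrong as written and should go; confidence in that is high. The culture-time part is a gap in control and not a demonstrated bias; confidence in it is medium. It becomes a bias only if the Day 6 share differs by ploidy, and the documents give neither the direction nor the size of such a difference.

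On the assumed ranges, the per-test false-positive rate is about 6-36% for shares of 30% v 40-50%, reaching about 53% in the most unfavourable case tried (0% v 20%), against 5% when shares are equal. These figures also ignore correlation between siblings. They show that the problem could matter, not that it will. For an exploratory pilot this is something the sponsor should correct, at low cost, before pairing begins.

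**What to change.** 1. Delete the miscarriage comparison. Replace it with a within-pair euploid v aneuploid table of sampling day, culture hours, stage and grade.
2. Add the exact sampling day (5 or 6), culture hours and hours since the last medium change to the control variables.
3. Pair same-day siblings where available. Otherwise keep the pair and include culture day or hours in the metabolite model.
4. As sensitivity analyses, report the same-day pairs alone, and a model that also adjusts for stage.

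The pairing rule should be fixed before the first pairs are formed: Methodology I has unselected samples destroyed at once and analysed samples destroyed after NMR, so pairs cannot be re-formed later.

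The cost is SAP wording, one recorded time per sample and a little extra analysis. Day and date are already on the label. No pairs are lost under the covariate option; the same-day sensitivity analysis will use fewer pairs, by a number the documents do not allow one to estimate.
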